6.2.1 Observed Cases Analysis

A mixed effects model for repeated measurements (MMRM) will be used to analyze the primary and continuous secondary efficacy endpoints. This model is based on the assumption that the missing data follow a missing at random (MAR) mechanism and uses only observed data. There are no imputations of missing data for this analysis.

6.2.2 Jump to Reference

A reference-based multiple imputation approach, jump to reference, may be used as a sensitivity analysis of the primary efficacy endpoint. This analysis is based on the assumption that the missing data follow a missing not at random (MNAR) mechanism. For this analysis, it is assumed that the distribution of values at future visits for patients in the CBD treatment group who discontinue early is similar to that of patients with observed data in the control arm.

No rules for outlier detection are planned.

7. Statistical Methods

7.1 General Principles

All data processing, summarization and analyses will be performed using Covance's SAS Environment / Version 9.4 (or later) of the SAS® statistical software package.

The analysis treatment group will be defined by the modal dose of study drug (dose of the study drug that the patient took for the longest period).

Statistical Analysis Plan

Sponsor Name: Insys Development Company, Inc.
Sponsor Protocol ID: INS011-16-085

Covance Study ID: 000000163564

The following principles will be applied to all TFLs unless otherwise stated:

Principle	Value
Significant tests	Two-sided and use a 5% significance level for main effects and 10% significance level for interaction terms
Treatment group labels and order presented	Listings: Placebo Cannabidiol Oral Solution (30 mg/kg/day) Cannabidiol Oral Solution (40 mg/kg/day) Tables: Placebo CBD (30 mg/kg/day) CBD (40 mg/kg/day) All CBD Total
Tables	Data in summary tables presented by treatment group and visit (where applicable)
Listings	All data collected presented by Treatment group Patient Visit (where applicable) Date; unless otherwise specified
Descriptive summary statistics for continuous variables	Number of patients/observations (n) Mean Standard deviation (SD) Median Minimum Maximum

COVANCE INC. CONFIDENTIAL

Document Date: 9 July 2018

Page 17 of 39
ST-AD-008 version 04

Downloaded by PPD on 10/12/2022

Statistical Analysis Plan

Sponsor Name: Insys Development Company, Inc.

Sponsor Protocol ID: INS011-16-085

Covance Study ID: 000000163564

Principle	Value
Descriptive summary statistics for categorical variables	Frequency counts and percentages [n (%)]
Denominator for percentages	Number of patients in the analysis population, unless stated otherwise in table shell(s)
Include "Missing" as category	Yes, when the number missing is greater than zero for at least one treatment group
Display for 0 percentages	Leave blank
Display to one more decimal place than collected value	Mean Mean Difference Median Percentages
Display to two more decimal places than collected value	Standard Deviation Confidence Interval
Limit of precision for displays	3 decimal places
Date Format	DDMMYYYY

Baseline is defined as the last scheduled or unscheduled measurement collected prior to first dose of double-blind investigational medicinal product (IMP) treatment.

Only data from scheduled post-baseline visits will be included in analyses and summary tables, all visit data will be listed.

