8.6. Statistical Analyses

8.6.1. Study Patients and Demographics

Analysis Treatment group will be defined by the modal dose of study drug (dose group the patient took for the longest period).

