2.2 Overall Study Design

This study is a double-blind, randomized, placebo-controlled, Phase 2 clinical trial in patients aged 8 to 17 years inclusive, with a genetically confirmed diagnosis of PWS.

Approximately 66 patients will be randomized in a 1:1 ratio to receive either:

- Cannabidiol Oral Solution (40 mg/kg/day) divided into twice daily doses with standard meal
- Matching placebo, divided into twice daily doses with standard meal

Randomization will be stratified according to use of growth hormone (Yes, No).

Patients will participate in the study for approximately 19 weeks. The study will consist of the following 6 periods:

- Screening Period (2 weeks)
- Placebo Lead-in Period (2 weeks)
- Titration Period (1 week)
- Maintenance Period (12 weeks)
- Taper Period (1 week)
- Follow-up Period (1 week)

Eligible patients will be assigned to a 2-week single-blind placebo lead-in period after which they will be randomly assigned to receive double-blind treatment with either Cannabidiol Oral Solution (40 mg/kg/day) or matching placebo (a 1-week Titration Period followed by a 12-week Maintenance Period). During the Titration Period Cannabidiol Oral Solution will be titrated as follows: Days 1-3: 20 mg/kg/day, Days 4-6: 30 mg/kg/day, Day 7: 40 mg/kg/day.

During the Maintenance Period, patients may have their dose of blinded study medication adjusted down to 30 mg/kg/day at the discretion of the investigator or qualified designee based on the patient's tolerability.

After completion of the study, patients will be offered an opportunity to enroll into an open-label, long-term safety study. Patients who do not elect to enroll in the long-term safety study will be titrated off study drug over 7 days and a final safety follow-up phone call will be placed 2 weeks after study completion for patients who do not elect to continue in the long-term safety study.

[figure not shown]
Statistical Analysis Plan

Sponsor Name: Insys Development Company, Inc.
Sponsor Protocol ID: INS011-16-085

Covance Study ID: 000000163564

The study design is depicted in [Figure 1](#).

Figure 1: Study Design Schematic

All screening, efficacy and safety evaluations will be performed according to the schedule of assessments summarized in [Appendix A](#).

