5.1 Intent-to-treat Population

The ITT population will consist of all randomized patients. ITT patients are analyzed according to their randomized treatment.

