5.2 Safety Population

The Safety population includes all randomized patients treated with at least one dose of the study drug during the double-blind treatment period. Safety patients are analyzed according to their actual treatment received.

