7.2 Subject Disposition and Data Sets Analyzed

Patient disposition will be listed and summarized by treatment group and overall and will include the number and percentage of patients:

- screened;
- entered placebo lead-in period;
- screened and not randomized;
- randomized (i.e. entered the titration period);
- randomized and not treated with double-blind treatment;
- treated with double-blind treatment;
- entered the maintenance period;
- entered the taper period;

COVANCE INC. CONFIDENTIAL

Document Date: 9 July 2018

Page 18 of 39
ST-AD-008 version 04

Downloaded by PPD on 10/12/2022

Statistical Analysis Plan

Sponsor Name: Insys Development Company, Inc.

Sponsor Protocol ID: INS011-16-085

Covance Study ID: 000000163564

- continued to the long-term safety study;
- included in each study population (Safety, ITT, PP, DEXA, PK).

In addition, the number and percentage of patients who complete the study and who discontinue early, including a breakdown of the primary reasons for discontinuation from the study will be presented.

A summary of patient randomization by site will also be provided by treatment group and overall for the ITT population. Inclusion/exclusion criteria not met will be listed for all screened patients.

In addition, a summary table and listing will be produced for discrepancies between the stratification factors in the database and IWRS. This will be produced for the ITT population.

A listing of study drug kit numbers and assignments will be produced.

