7.4 Demographics and Other Baseline Characteristics

Demographic and baseline characteristics will be listed and summarized by treatment group and overall for the ITT population. Standard descriptive statistics will be presented for:

- age (years) [calculated as (screening visit date – date of birth)/365.25 and reported as whole years];
- gender (Male, Female);
- ethnicity (Hispanic or Latino, Not Hispanic or Latino, Unknown);
- race (White, Black or African American, Asian, American Indian or Alaska Native, Native Hawaiian or other Pacific Islander, Other);
- weight (kg) at Screening visit;
- body mass index (kg/m^2) (derived on eCRF);
- randomization strata of growth hormone treatment (Yes, No).

No formal tests of statistical significance will be performed on the demographic and baseline data.

Statistical Analysis Plan

Sponsor Name: Insys Development Company, Inc.

Sponsor Protocol ID: INS011-16-085

Covance Study ID: 000000163564

Other baseline measurements, such as vital signs and ECG, will be summarized by treatment group with the post-baseline measurements.

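### The analysis group is set by modal dose, so ITT descriptive tables show a CBD 30 column to which nobody was randomized, and adverse events can be counted under a dose the patient was not taking

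*SAP*

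**What the plan says.** - SAP 7.1, for tables, figures and listings in general: "The analysis treatment group will be defined by the modal dose of study drug". Table columns are Placebo, CBD 30, CBD 40, All CBD and Total. Listings have Placebo, CBD 30 and CBD 40 only.
- Protocol 8.6.1 carries the same rule: "Analysis Treatment group will be defined by the modal dose of study drug (dose group the patient took for the longest period".
- SAP 2.2: "Approximately 66 patients will be randomized in a 1:1 ratio to receive either" CBD 40 mg/kg/day or matching placebo. Under Protocol 3.5, 30 mg/kg/day in Maintenance comes only from a reduction for tolerability.
- SAP 5.1: "ITT patients are analyzed according to their randomized treatment".
- SAP 5.2: "Safety patients are analyzed according to their actual treatment received".
- Tables tied to the ITT population and split by treatment group include baseline (SAP 7.4: "Demographic and baseline characteristics will be listed and summarized by treatment group and overall for the ITT population") and randomization by site (SAP 7.2: "A summary of patient randomization by site will also be provided by treatment group and overall for the ITT population").
- SAP 7.6 and 7.6.4 confine inference to placebo versus All CBD, but call for 30 and 40 columns in the descriptive efficacy tables.
- SAP 7.7.2 tabulates TEAEs by treatment group, including those causing discontinuation, and has no rule tying an event to the dose being taken when it began.
- SAP 7.2 expects some patients to be "randomized and not treated with double-blind treatment".

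**The concern.** The modal dose depends on what happens after randomization: whether the patient tolerates 40 mg/kg/day, when the dose is reduced and when treatment stops. Using it as the default grouping has three consequences.

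1. **ITT descriptive tables.** The baseline, randomization-by-site and descriptive efficacy tables would show a CBD 30 column to which nobody was randomized. It is selected on tolerability and stands beside a placebo column that is left unsplit, although blinded dose can be reduced in that arm too. Neither CBD dose column has a like-for-like comparator.
2. **Adverse events by dose.** All of a patient's events go under one dose. An event that starts on 40 and prompts an early reduction is counted under 30. An event on 30 after a late reduction is counted under 40. The 40 column can therefore understate or overstate what happened on that dose.
3. **Patients without a dose group.** Those who stop during titration or just after it, and those never treated, may fit no dose column. The first of these include the patients with the earliest intolerance.

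**Working it through.** The plan states no figure on this point, so the check is a count of days at each dose.

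**Inputs.** 20 mg/kg/day on Days 1–3, 30 on Days 4–6 and 40 from Day 7 (SAP 2.2); reduction from 40 to 30 allowed in Maintenance (Protocol 3.5). Assumed: dosing to Day 91 (13 weeks × 7 days), and all days at a dose added together, including the three titration days on 30. Taper days are left out. For a completer they do not change the label: a reduced patient tapers through 20 only (Protocol 4.1.5), and an unreduced patient has 91 − 6 = 85 days on 40 against 3 + 3 = 6 on 30.

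**Formula.** Let t be the last day on 40 and T the last dosing day.

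- Days on 40 = t − 6
- Days on 30 = 3 + (T − t)
- The label is CBD 30 when 3 + (T − t) > t − 6, that is, when t < (T + 9)/2

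**Results at T = 91**, where (91 + 9)/2 = 50:

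| Last day on 40 | Days on 30 | Days on 40 | Label |
|---|---|---|---|
| Day 49 | 3 + 42 = 45 | 43 | CBD 30 |
| Day 50 | 3 + 41 = 44 | 44 | tie, no rule |
| Day 51 | 3 + 40 = 43 | 45 | CBD 40 |

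In the first row, events from 43 days on 40 are counted under CBD 30, including the one that led to the reduction. In the third row, events from 40 later days on 30 are counted under CBD 40.

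**Other reading of the rule.** If the longest unbroken run decides, the comparison is T − t against t − 6, and the cut-point is (91 + 6)/2 = 48.5. Last day on 40 = Day 49 then gives 42 days against 43 and the label CBD 40; Day 48 gives 43 against 42 and CBD 30. The cut-point moves by about one day, and misattribution in both directions remains.

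**Discontinuation after a reduction.** Take t = 40 and T = 60. Days on 40 = 34; days on 30 = 3 + 20 = 23 (20 as an unbroken run). On either reading, an event on 30 that ends treatment on Day 60 is counted under CBD 40 in the discontinuation table.

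**Early stops without a reduction** (the two readings agree here):

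| Last dosing day | Days on 20 / 30 / 40 | Modal dose |
|---|---|---|
| 3 | 3 / 0 / 0 | 20 |
| 5 | 3 / 2 / 0 | 20 |
| 6 | 3 / 3 / 0 | tie 20/30 |
| 8 | 3 / 3 / 2 | tie 20/30 |
| 9 | 3 / 3 / 3 | three-way tie |
| 10 | 3 / 3 / 4 | 40 |

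Days 1–5 give modal dose 20, which has no table column or listing group. Days 6–9 give ties. The tolerability calls fall on Days 3 and 6, and patients who do not tolerate 20 or 30 are discontinued (Protocol 4.1.3 and 7.3.1), so these are foreseeable stopping days. Randomized but untreated patients have no modal dose. The SAP does not say whether any of these patients belong to All CBD.

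**The case against.** The strongest reply is that the 30 and 40 columns only subdivide the CBD arm. Nobody crosses between arms, All CBD is a standing table column, and every test compares placebo with All CBD. That is right, and it limits the point to descriptive tables. It does not remove the conflict: SAP 7.1 allows exceptions where otherwise stated, but SAP 7.6 and 7.6.4 themselves order dose columns for efficacy data that SAP 5.1 assigns by randomized treatment.

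For safety, modal dose can be defended as a working definition of treatment received, and events can be traced. All adverse event and administration data are listed, and the action taken, including dose modification, is recorded (Protocol 6.2.6.2). This stands for individual cases. A reader of the summary tables would still see the counts under the modal dose, and the listings lack a group for the patients described above.

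A reader might infer that the dose columns are the only planned look at dose and safety. They are not: Protocol 8.6.5 plans an exposure-response analysis that includes safety endpoints, and SAP 7.8 refers to a separate PK SAP. They are the SAP's planned tabulation of adverse events by dose. Nor can one say that titration stops will appear only under All CBD or Total, because All CBD membership is not defined for them.

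**Conclusion.** The point holds for the descriptive ITT tables and for adverse events tabulated by dose. Followed as written, the rule creates a post-randomization column in ITT displays, counts some events under a dose the patient was not taking, and leaves some patients without a dose group.

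The day counts assume dosing to Day 91 and added days; the unbroken-run reading shifts the cut-point by about one day and does not change the conclusion.

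Two stronger readings are not supported. One is that the primary or secondary tests are biased: they use placebo versus All CBD, and the dose split does not enter them. The other is a count of affected patients. Protocol 1.3.3 reports reductions in 9 of 20 patients at 40 mg/kg/day in a study of about 48 weeks. That was an open-label, flexible-dose epilepsy study and the protocol does not say when the reductions came. It shows that reductions are foreseeable, but the number in this population is unknown. The issue is worth correcting before unblinding, so that ties and unclassified patients are not settled with the data in view.

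**What to change.** In SAP 7.1:

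1. Define the analysis group as the randomized arm for ITT tables, and as CBD or placebo actually received for safety tables and for listings.
2. Define All CBD as every patient randomized to CBD (ITT) or who received any CBD (safety), whatever dose was reached. Make placebo versus All CBD the main columns.
3. Keep modal-dose columns only as supplementary displays labelled non-randomized, with a stated counting rule (added days or unbroken run), a tie rule and a titration-dose category.
4. In any by-dose TEAE table, assign each event to the dose in effect at onset or worsening. Show taper and post-treatment events in a separate category; otherwise follow-up events in tapered patients would fall under the taper dose. State a rule for partial onset dates, and give the patients and exposure time at each dose as denominators.

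Align Protocol 8.6.1 at the next amendment, or record the departure in SAP section 8, which now lists no changes.

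The cost is a few more derivations and table-shell edits. The Placebo, All CBD and Total columns are already planned, administration dates and times are in the CRF (Protocol 4.4), and modal dose already needs each patient's dose history. No patients or procedures are added, and the tested contrast is unchanged. The dose-at-onset display remains descriptive and confounded by time on treatment.

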3.6. Stopping Rules

The Investigator reserves the right to terminate the study in the interest of patient safety and welfare. The Sponsor reserves the right to terminate the study at any time for administrative reasons. Patients will also be discontinued when their liver enzymes and serum bilirubin reach:

- ALT or AST > 8 x ULN
- ALT or AST > 5 x ULN for more than 2 weeks
- ALT or AST > 3 x ULN and (TU>2 x ULN or INR>1.5)
- ALT or AST > 3 x ULN with appearance of fatigue, nausea, vomiting, right upper quadrant pain or tenderness, fever, rash, and/or eosinophilia (> 5%)

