6.2.3. Vital Signs

Vital signs (seated blood pressure, pulse rate, temperature and respiration rate) will be measured at every visit: Screening (Visit 1), Placebo Lead-In (Visit 2), Baseline (Visit 3), Titration Period (Visit 4), Maintenance Period (Visits 5, 6, 7, 8, 9), and Study Completion/Early Withdrawal (Visit 10) Visits.

Additional vital sign measurements may be performed as deemed medically necessary by research personnel.

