6.2.6. Adverse Events and Serious Adverse Events

6.2.6.1. Definition of Adverse Events

An AE is defined as any untoward medical occurrence in a patient administered a pharmaceutical product during the course of a clinical investigation. An AE can therefore be any unfavorable

and unintended sign, symptom, or disease temporally associated with the use of an investigational product, whether or not thought to be related to the investigational product.

Patients will be monitored throughout the study for AEs. Monitoring for treatment-emergent AEs (TEAEs) will begin as soon as the patient is dosed. All AEs must be followed until they are resolved or stabilized, or until all attempts to determine resolution of the event are exhausted. The investigator should use their discretion in ordering additional tests as necessary to monitor the progress of such events.

An AE may be:

- A new illness, not documented in the patient's medical history;
- Worsening of a concomitant illness;
- An effect of the study medication; it could be an abnormal laboratory value, as well as a significant shift from baseline within normal range which the qualified investigator or medical qualified designate considers to be clinically important;
- A combination of two or more of these factors.

Surgical procedures themselves are not AEs. They are therapeutic measures for conditions that require surgery. The condition for which the surgery is required is an AE, if it occurs or is detected during the study period. Planned surgical measures permitted by the clinical study protocol and the condition(s) leading to these measures are not AEs, if the condition(s) was (were) known before the start of study treatment. In the latter case, the condition should be reported as medical history.

Weight gain or loss will not be recorded as an AE. Hyperphagia behaviors and skin picking will not be recorded as AEs; however, any other behaviors may be recorded as AEs based on the Investigator's opinion.

Patients will be monitored throughout the study for AEs. All AEs must be followed until they are resolved or stabilized, or until all attempts to determine resolution of the event are exhausted. The investigator should use his/her discretion in ordering additional tests as necessary to monitor the progress of such events.

Adverse events reported prior to dose administration will be recorded as part of the patient's medical history.

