9.4.3. Source Documents

All information recorded in the CRF/EDC system must be supported by corresponding source documentation. Examples of acceptable source documentation include, but are not limited to, hospital records, clinic and office charts, laboratory notes, and recorded data from automated instruments, memoranda, and pharmacy dispensing records.

During the study, select CRF/eCRF data may be used as original data collection tools as long as a description of this documentation process is maintained in the investigator's study files. Clinical laboratory data required by the protocol will be electronically transferred from the local laboratory to the sponsor or the sponsor's representative. A paper copy of the laboratory results will be provided to the study site and should be retained with each patient's source data.

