7.7.3 Laboratory Evaluations

7.7.3.1 Standard Safety Laboratory Panel

Data for the following hematology, blood chemistry, and urinalysis analytes received from central laboratory will be listed and summarized by treatment group and visit. If data for any additional analytes are also received or recorded, then these will be listed only.

Hematology	Serum Chemistry	Urinalysis
Hemoglobin	Albumin	pH
Hematocrit	Blood Urea Nitrogen	Specific Gravity
Total Leukocyte Count	Creatinine	Protein
Differential Leukocyte Count	Total Bilirubin	Glucose
Red Blood Cell Count	Alkaline Phosphatase (ALP)	Ketones
Platelets	Aspartate Transaminase (AST)	Bilirubin
Neutrophils (abs, %)	Alanine Transaminase (ALT)	Blood
Lymphocytes (abs, %)	Sodium	Nitrite
Monocytes (abs, %)	Potassium	Leukocyte Esterase
Eosinophils (abs, %)	Chloride	Urobilinogen
Basophils (abs, %)	Lactate Dehydrogenase (LDH)	Color and Clarity
White Blood Count	Uric Acid	Microscopic
	Glucose	Urine T. Protein, Random
	Calcium	Urine Creatinine, Random

All laboratory data will be reported in Conventional units. Out-of-reference-range values will be flagged as high (H) or low (L) in the listings.

For analysis purposes, values preceded by a "<" or a ">" sign (i.e. those below or above the limits of quantification) will be considered equal to the lower or upper limit of quantification, respectively.

Laboratory and urinalysis data will be summarized by visit using standard descriptive statistics for the Safety population. Changes from baseline will also be summarized.

Statistical Analysis Plan

Sponsor Name: Insys Development Company, Inc.

Sponsor Protocol ID: INS011-16-085

Covance Study ID: 000000163564

For hematology and serum chemistry, shift tables presenting movement in and out of reference ranges from baseline to each scheduled post-baseline visit will be provided for each treatment group. Corresponding shift tables will be produced for urinalysis.

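### SAP 7.1 keeps unscheduled post-baseline values out of the by-visit and shift tables, and with only one scheduled post-baseline chemistry sample a peak liver value may appear in listings alone

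*SAP*

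**What the plan says.** The general rule is in SAP 7.1: "Only data from scheduled post-baseline visits will be included in analyses and summary tables, all visit data will be listed". The same section treats the pre-dose side differently: "Baseline is defined as the last scheduled or unscheduled measurement collected prior to first dose".

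The safety sections follow the rule. SAP 7.7.3.1 plans "shift tables presenting movement in and out of reference ranges from baseline to each scheduled post-baseline visit" for hematology and chemistry, plus descriptive statistics by visit. SAP 7.7.4 and 7.7.5 summarize vital signs and ECG by visit. SAP 6.1 uses nominal visits without windows, so an extra sample is not moved into a scheduled slot. No worst-post-baseline table or liver-threshold table is planned.

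Protocol 3.6 sets four liver limits for discontinuing a patient, the first being "ALT or AST > 8 x ULN". Protocol 6.2.5.2 and footnote d of protocol Table 1 schedule chemistry at Screening and at Visit 10/Early Withdrawal only. The Week 3 laboratory entry in that table is a blood count.

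The protocol allows for extra measurements. On adverse event follow-up, section 6.2.6.1 says: "The investigator should use their discretion in ordering additional tests as necessary to monitor the progress of such events". On vital signs, section 6.2.3 says: "Additional vital sign measurements may be performed as deemed medically necessary by research personnel".

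The two documents also name different laboratory sources. SAP 7.7.3.1 covers "analytes received from central laboratory will be listed and summarized by treatment group and visit", while protocol 9.4.3 has results "electronically transferred from the local laboratory".

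**The concern.** Safety and tolerability is a stated secondary objective, and the liver limits in protocol 3.6 are the only numerical safety thresholds on which a patient is discontinued. A reader of the study report will look in the laboratory tables for how many patients in each arm had large transaminase elevations and how large these were. If the qualifying value came from an unscheduled sample, the scheduled-only rule removes it from those tables, and no other planned table gives its size. The comparison between arms on this question would have to be assembled by hand from listings.

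**Working it through.** The plan states no figure to reproduce here. The check counts scheduled samples and compares them with what each limit needs.

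**1. Scheduled post-baseline assessments.** Inputs: protocol Table 1 with footnote d, protocol 6.2.3 to 6.2.5, and SAP Appendix A. Week k is taken as Day 7k, so Week 13 is Day 91. The gap is the difference between consecutive scheduled days, starting at Day 1.

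| Assessment | Scheduled days | Count | Longest gap |
|---|---|---|---|
| Chemistry (ALT, AST, bilirubin) | 91 | 1 | 91 − 1 = 90 days |
| Blood count/hematology | 21, 91 | 2 | 91 − 21 = 70 days |
| ECG | 35, 63, 91 | 3 | 35 − 1 = 34 days |
| Vital signs | 7, 21, 35, 49, 63, 77, 91 | 7 | 14 days |

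Any liver elevation detected between Day 1 and Visit 10/Early Withdrawal must therefore come from an unscheduled sample.

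**2. The protocol 3.6 limits against the scheduled data.**

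- *Above 8 x ULN.* One value is enough, but scheduled data show it only if it is present at Visit 10/Early Withdrawal.
- *Above 5 x ULN for more than two weeks.* This needs at least two values more than 14 days apart. One scheduled post-baseline sample cannot show it. Screening cannot supply the first value, because inclusion criterion 8 caps ALT and AST at 3 x ULN.
- *Above 3 x ULN with a second marker.* Bilirubin is in the chemistry panel, again with one scheduled sample. (The protocol abbreviates this marker as TU without defining it. I read it as total bilirubin, because the lead-in sentence names serum bilirubin.) INR, the alternative marker, is in neither protocol 6.2.5 nor the SAP 7.7.3.1 panel, and SAP 7.7.3.1 sends additional analytes to listings.
- *Above 3 x ULN with symptoms or eosinophilia.* This needs the transaminase value joined to adverse event or differential-count data. No planned table does so.

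**3. Tracing one hypothetical patient** with ALT at 9 x ULN on an unscheduled test:

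| Output | Is the patient or value there? |
|---|---|
| Laboratory listing | Yes, flagged high |
| By-visit laboratory statistics | Not the peak; only the Visit 10/Early Withdrawal value, if obtained |
| Laboratory shift table | The same |
| Disposition (SAP 7.2) | Yes, if withdrawn, with a primary reason |
| TEAE tables (SAP 7.7.2) | Yes, if recorded as an adverse event; graded mild, moderate or severe |
| Count by protocol 3.6 limit | No such table |

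**4. What the planned tables show of a scheduled peak.** The shift table records only movement in and out of the reference range. A child already above range at entry, which inclusion criterion 8 allows up to 3 x ULN, can only appear as high-to-high. The by-visit maximum does show the highest scheduled value.

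**The case against.** A reader might infer that a stopping-rule case disappears from every summary table. The documents do not support that. SAP 7.7.2 defines TEAEs by date, not visit type, and tabulates them by preferred term, severity and discontinuation. Protocol 6.2.6.1 allows an abnormal laboratory value to be an adverse event if the investigator considers it clinically important. SAP 7.2 tabulates reasons for discontinuation. Protocol 3.4 and 7.4.2 call for end-of-study evaluations, including chemistry, at premature discontinuation where possible, and SAP Appendix A places these in the Visit 10 column. All of this stands. It means the patient is usually counted somewhere. It does not give the size of the elevation or the limit met, and the withdrawal sample may miss the peak.

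Nor does the protocol show that the worst values are the ones most likely to be unscheduled. The sentence on additional tests in section 6.2.6.1 concerns following events already identified as adverse events, and the vital-signs sentence is only permissive. For liver tests the argument rests on the schedule alone, which is enough.

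It is also tempting to put a rate on the loss: one or two of 33 CBD patients would be 1/33 = 3.0% or 2/33 = 6.1%, reported as zero. Those are hypothetical cases, and the SAP plans no threshold rate that could read zero. Extending the stopping-rule argument to QTcF or blood pressure also fails: no protocol 3.6 limit uses either, and they have three and seven scheduled post-baseline assessments.

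Finally, the SAP delivers the laboratory analyses the protocol promises (observed values, changes and normal-range shifts). In a trial of about 66 patients with descriptive safety reporting, a few cases can be counted from listings ordered by treatment group. That limits the harm, but leaves an avoidable hand count for the protocol's own liver limits.

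**Conclusion.** The point holds in a limited form. Unscheduled post-baseline laboratory, ECG and vital-sign values are left out of the by-visit and shift tables and are only listed. This has practical weight for liver tests, where there is one scheduled post-baseline sample, up to about 90 days after Day 1. A peak that meets a protocol 3.6 limit before then would normally be unscheduled and may be missing from the laboratory tables, and the sustained-elevation limit cannot be shown from scheduled data at all. The effect is weaker for ECG and weakest for vital signs.

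How many patients this would affect cannot be estimated from the documents. The conclusion assumes that SAP 7.1 is applied as written, and that unscheduled results reach the database, as its promise to list all visit data implies. The plan should be changed on this point, but safety reporting does not fail as a whole. The difference between central and local laboratory data is a separate inconsistency and does not depend on the scheduled-only rule.

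**What to change.** 1. In SAP 7.1, restrict the scheduled-only rule to by-visit summaries and efficacy analyses.
2. In SAP 7.7.3.1, add a worst-post-baseline shift table for liver tests, using all scheduled and unscheduled results in the database. As a lesser addition, do the same for other laboratory parameters and ECG.
3. Add one table, placebo versus all CBD, of patients who ever met each protocol 3.6 liver limit that can be evaluated from collected data. Footnote that INR is not in the planned panel and is counted only where obtained, and define the bilirubin term used in the programming.
4. Separately, reconcile the central laboratory of SAP 7.7.3.1 with the local laboratory of protocol 9.4.3, and state which results enter the tables.

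The cost is SAP wording, one derived record per parameter and one or two extra descriptive tables. No additional sampling is needed and the limits in protocol 3.6 are untouched, but the INR part of the count will be incomplete wherever INR was not measured.
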